7.2 Methods and Timing for Assessing, Recording, and Analyzing Safety Parameters

Adverse Events tracking is highly recommended for pain research based on IMMEDIATE recommendations (Turk et al., 2003) and will be tracked, monitored, and adjudicated for this research in accordance with **Appendix J**. Physical Therapy and Psychotherapy treatment providers will maintain regular clinical notes input within 24 hours of each appointment into the VA Electronic Medical Record (in accordance with **Appendix K**). These data will be discussed and analyzed during the weekly research meeting with the PI and Co-Investigators during which the risk profile will be determined and addressed.

Behavioral health interventions for chronic pain tend to be safe compared to medical interventions (Morley et al., 1999). Although there are data describing the adverse effects associated with introducing opioid medications to a pain management program (see Moore & McQuay, 2005), there is little in the extant literature describing the risks of opioid sparing in the context of a program like the OSI (including risk for opioid recidivism and withdrawal symptoms). Indeed, data from the original FORT trial did not reveal any adverse consequences of opioid reduction among those who voluntarily suspended opioid medication use.

A comprehensive review of Physical Therapy outcomes among military PT service recipients covering 472,013 PT visits across 40 months revealed no significant adverse effects of PT for active duty and Veteran patients seeking PT services (Moore et al., 2005). However, Carlesso and colleagues (2010) suggest that this negative finding is likely a function of poor adverse event surveillance in research utilizing PT. The STRONG STAR Consortium recently published a description of Adverse Events monitoring guidelines and recommendations for behavioral health trials including a PTSD diagnosed population (Peterson et al., 2013). These recommendations have been incorporated into the risk monitoring procedures used for the proposed study.

7.3 Adverse Events and Serious Adverse Events

*An **adverse event (AE)** is generally defined as any unfavorable and unintended diagnosis, symptom, sign (including an abnormal laboratory finding), syndrome or disease which either occurs during the study, having been absent at baseline, or if present at baseline, appears to worsen. Adverse events are to be recording regardless of their relationship to the study intervention.*

*A **serious adverse event (SAE)** is generally defined as any untoward medical occurrence that results in death, is life threatening, requires inpatient hospitalization or prolongation of existing hospitalization, results in persistent or significant disability/incapacity, or is a congenital anomaly.*

AEs and SAEs may be related directly to research participation or unrelated to research. Potential research-related AEs and SAEs for this study include the following:

Adverse Event	Serious Adverse Event
---------------	-----------------------

Research Related	Increased PTSD symptoms Increased pain intensity Increased emotional distress Opiate withdrawal symptoms	Increased Suicidal Risk Hospitalization for mood or pain
Research Unrelated	Example: Flu	Example: New Injury

All AE and SAE monitoring will be completed using the STRONG STAR procedures for Adverse Events Monitoring, Documentation, and Adjudication (**Appendices J, L, and M**). Any study member who identifies an AE or SAE will immediately report it to the study coordinator and begin the process for prompt reporting to the IRB pursuant to the SOP. SAE and AE report forms (see attachment SOPs) will be forwarded to STRONG STAR Regulatory Personnel who will prepare the official report to the IRB. Each participant chart includes an AE/SAE tracking form in which AEs and SAEs will be documented by hand as soon as they are identified (per the SOP)

Adverse events will be monitored through the following mechanisms:

AE/SAE	Assessment Tool	Notes
PTSD Symptoms	PCL-5	Given at every assessment interval and at every individual PTSD treatment session for FORT-A participants Clinical significant change for the PCL-5 has not yet been established, so we will use a 20-point increase in symptoms as a clinically significant indicator of PTSD symptoms (based on the previous version of the PCL; see Appendix N)
Pain Intensity	Numeric Rating Scale (NRS)	Assessed at every assessment interval and at every physical therapy appointment for FORT-A participants Opinions vary on a clinically meaningful change in pain numeric rating, but many agree that an increase in pain rating > 2 points is clinically significant (see [name] et al., 2006)
Emotional Distress	PHQ-9	Given at every assessment interval and once a week during group treatment

		
sessions for FORT-A participants
 
Change in PHQ-9 scores is clinically significant if the total score rises above 15 (as defined in Kroenke & Spitzer, 2002). Those who begin the study with a score above 15 show significant change (requiring AE report) if the score rises 5 points or more. If item #9 increases at all, this will be reported an AE. An increase of Item #9 by 2 points or more will be considered a SAE.

Opiate Withdrawal	SOWS	
The Subjective Opiate Withdrawal Scale will be given to all FORT-A participants once a week during treatment and at all assessment intervals for all follow-up intervals. A SOWS score of 11 or more will indicate an AE requiring follow-up (based on established cut-off scores).

This study maintains a weekly research meeting (starting September 2015; currently set for Thursday morning from 1030-1100 at the STRONG STAR Conference Room with an open phone line for those who need to call into the meeting) to discuss research progress and to discuss participant status and flow throughout the research process. All Adverse Events (AEs) and Serious Adverse (SAEs) will be discussed at these meetings (attended by all study staff). To protect blinding, participants will be discussed by unique identifier only.

AE reporting procedures (as described in the attached SOP) will begin immediately after an AE is noticed and will be reported to the IRB after discussion at the weekly research meeting. SAEs must be reported to the IRB within 24-48 hours. If a protocol deviation, SAE or UPIRSO is not reported within 48 hours, a reason will need to be documented on the P50 form.

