4.1 Inclusion Criteria

Study participants must meet all of the inclusion criteria below to participate in this study as follows:

- 1) Demographics for inclusion in this research include both genders, all racial/ethnic groups, and ages 18-72.
- 2) Present with chronic musculoskeletal pain (CMP) as a primary pain complaint
- 3) CMP is accompanied by at least moderate disability based on a score of 20% or more on the Oswestry Disability Index;
- 4) Consistent with NIH Task Force recommendations, "chronic" CMP has been a problem for the Veteran for at least half the days in the last 3 months and was acquired or exacerbated as part of active duty U.S. military service in the Gulf War, Operations Iraqi Freedom (OIF), Enduring Freedom (OEF), or New Dawn (OND) war eras.
- 5) CMP presents in the context of comorbid psychiatric symptoms of posttraumatic stress disorder (PTSD; based on a score of 25 or more on the PTSD Checklist-Version 5) and/or depression (based on a score of 10 or more on the PHQ-9).

6) Demonstrate prior “chronic” opioid use (defined as using opioid medication for 20 out of every 30 days over three or more months) and discharged off of persistent opioid medications on their own or by a provider for at least one week prior to the pain management program period (Weeks 1-3).

7) Speak and read/understand English well enough to fully participate in the intervention and to reliably complete assessment measures.

8) The Veteran will be eligible to be a PRC patient (i.e., have multiple trauma related physical and psychological injuries; VA, 2013) and be eligible for Physical Therapy referral through the PRC (though the referral for the same service could also come from another VHA provider). All participants will be offered Physical Therapy services before enrollment and will be enrolled after completing or denying Physical Therapy.

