Depressive Symptom Inventory- Suicidality Subscale (DSI-SS) (suicidal ideation or intent)		Risk Surveillance Suicide risk is not a research endpoint, but if suicide risk is present at a previous assessment (e.g., any positive response for BSSI screening items) then BSSI will be repeated at the next assessment interval (unless participant is disenrolled for a VA mental health treatment referral)
Functional Capacity Evaluation (objective disability)		Endpoint: Hypothesis 2 Assess at all assessment intervals
Pain Catastrophizing Scale (pain-related cognitions)		Endpoint: Hypothesis 2 Variable: Exploratory
Interpersonal Needs Questionnaire (Burdensomeness)		Endpoint: Hypothesis 2 Variable: Exploratory
Fear Avoidance Beliefs Questionnaire		Endpoint: Secondary Objectives Variable: Exploratory
Chronic Pain Acceptance Questionnaire	Endpoint: Secondary Objectives	

		Variable: Exploratory
Multidimensional Pain Inventory		Endpoint: Secondary Objectives Variable: Exploratory
Generalized Anxiety Disorder- 7 item		Endpoint: Hypothesis 2 Assess at all assessment intervals
Current Opioid Misuse Measure		Endpoint: Hypothesis 4 Assess at all assessment intervals
Actiwatch		Endpoint: Hypothesis 2 Assess at all assessment intervals
MEMS eCap		Endpoint: Hypothesis 4 Assess at all assessment intervals
Treatment Helpfulness Questionnaire		Endpoint: Secondary Objectives Variable: Exploratory Only given post-treatment
Subjective Opiate Withdrawal Scale		Endpoint: Hypothesis 4 Assess post-treatment and at follow-ups
Pain Diary		Endpoint: Hypothesis 2 Assess at all assessment intervals
Phone Contact (Adherence/AE/MEMS/Actiwatch)		Treatment Adherence Occurs at all assessment intervals
Quick Drinking Scale (QDS)		Common Data Element with STRONG STAR Studies
Fagerstrom Test for Nicotine Dependence (FTND)		Common Data Element with STRONG STAR Studies
Fagerstrom Test for Nicotine Dependence – Smokeless Tobacco (FTNB-ST)		Common Data Element with STRONG STAR Studies

Randomization

As noted above, participants will be randomly assigned to the FORT-A or PRC on a 1:1 allocation ratio using a randomly selected block size with randomly permuted assignments within blocks.

In the original FORT study we found that the ideal treatment group size for each iteration of the program was 5 participants (though successful groups were able to run with as few of 3 members and as many as 7). Thus, we will attempt to fill treatment

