6.2.4 Followup Visits (see Figure 4)

Follow-up assessments will occur in the following intervals:

Visit	Measure	Assessment Window
Visit 2 (Baseline)	Psychosocial Assessment Pain Diary Functional Capacity Evaluation (FCE) Upload Actiwatch Provide and Train for MEMS Adverse Events Opioid/Medication Assessments (TLFB/SOWS/COMM/Concomitant Medications) MQS STRONG STAR Common Data Elements	≤ 2 weeks before treatment
Visit 14 (Post-Treatment)	Psychosocial Assessment Pain Diary FCE	≤ 2 weeks after treatment

	Upload Actiwatch Upload MEMS Adverse Events Opioid/Medication Assessment MQS STRONG STAR Common Data Elements	
Phone Assessments 1-11	Opioid/Med Assessment (TLFB) MQS	Monthly ± 1 week
Visit 15 (Six-Month Follow-Up)	Psychosocial Assessment Pain Diary FCE Upload Actiwatch Upload MEMS Adverse Events Opioid Assessment/Medication MQS STRONG STAR Common Data Elements	± 24 weeks after treatment ± 2 weeks

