9.4 Interim Analyses and Stopping Rules

Interim analyses will not be completed as part of this research. We were fortunate to have solid data from the original FORT trial to help estimate power for the proposed research, and the resulting power analyses are solid. Thus, we do not anticipate uncovering changes in the primary outcome that would necessitate a need for early stoppage or futility of the proposed research and do not feel that we have any preliminary impetus for spending alpha in pursuit of these interim analyses. In conclusion, we do not anticipate observing evidence for early futility or superiority in this trial until all data are gathered in accordance with our in-place power analysis.

The interventions used in this study have been thoroughly studied in other research and it is predicted that the need for a safety review will be low. However, there are some circumstances that would require suspension of study activity and review of safety by an ad hoc safety review committee as follows:

- This is one of the first studies of an interdisciplinary pain program for chronic pain and trauma polymorbidity. The PIs STRONG STAR Pain and PTSD Study revealed no significant exacerbation of PTSD symptoms in a combined pain and PTSD protocol, but PT was not involved in that protocol. There is no reason right now to believe that Physical Therapy will exacerbate PTSD symptoms, but if this were to occur (based on a 20 point increase on the PCL-5) then a safety review would be needed to determine if the study must stop. This finding would also need to be adjudicated through the AE process.
- As noted above, opioid withdrawal effects will be monitored, and a score above 11 on the SOWS will require safety review.
- If physical injury or emotional disruption AEs accumulate (more than 4 minor; easily recovered within one day – or 2 major; requiring more than ASAP intervention to stabilize) then a safety review will be in order.

Such findings are presented to the study statistician or to the Independent Monitoring Committee (IMC) statistician to review the events by group to determine whether there are statistical as well as clinical concerns. The statistician reports his findings to a closed session of the IMC or to the Safety Officer and/or NCCIH. The findings are used to determine what steps will be taken.

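### The SOWS rules in 7.3 and 9.4 have no baseline term, so withdrawal that is unchanged or improving since entry is recorded as an adverse event and can trigger safety review

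*Combined protocol and SAP*

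**What the plan says.** Section 7.3 gives a baseline-referenced definition of an adverse event: one "which either occurs during the study, having been absent at baseline, or if present at baseline, appears to worsen". The monitoring table in the same section sets a rule for each tool. For SOWS it is: "A SOWS score of 11 or more will indicate an AE requiring follow-up".

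Section 9.4 introduces its list of triggers by saying that "there are some circumstances that would require suspension of study activity and review of safety by an ad hoc safety review committee". One item on that list is that "a score above 11 on the SOWS will require safety review". Events that meet a trigger go to a statistician for review by group.

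The other rows of the 7.3 table read differently. For PTSD symptoms, "we will use a 20-point increase in symptoms as a clinically significant indicator of PTSD symptoms". The pain row uses an increase of more than 2 points. The PHQ-9 row uses a rise above 15, and for participants who start above 15 it requires a further rise of 5 points or more.

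On timing, the schedule in 6.1 marks SOWS at baseline and the Visit 2 list in 6.2.4 includes it. The SOWS line of the baseline table in 6.2.2 instead carries the note "Assess post-treatment and at follow-ups".

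Criterion 6 in 4.1 asks for at least one week off opioids before the program weeks. Section 6.1 allows the baseline assessment up to 2 weeks before treatment.

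**The concern.** An absolute cut-off cannot tell withdrawal that a participant brought into the trial from withdrawal that arose or worsened in it. The definition in 7.3 draws exactly that distinction. The SOWS row and the 9.4 trigger do not, although every other tool in the table does so in some way.

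The population makes this more than a drafting point. All participants are former persistent opioid users, and some may have stopped only a week before the program, so scores at or above the cut-off at entry are foreseeable. Followed as written, the SOWS row would record such a participant as having an AE at a later visit even if the score had not moved or had fallen. A score above 11 would also meet a condition that 9.4 links to suspending study activity. The withdrawal AE count would then mix two different things, and a reader of the safety tables could not separate them.

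**Working it through.** The plan states no figure that depends on this point, so there is nothing to reproduce. The check is a comparison of the rules, followed by an illustration of size.

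**Step 1. The four tools in the 7.3 table.**

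| Tool | Rule | How entry level is handled |
|---|---|---|
| PCL-5 | 20-point increase | change score |
| Pain NRS | increase of more than 2 points | change score |
| PHQ-9 | rise above 15 | if above 15 at entry, a further rise of 5 or more |
| SOWS | 11 or more | no provision |

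PHQ-9 is the closest parallel. It also uses a cut-off, and it deals expressly with people who are already over it. In the 9.4 list, too, the PCL-5 trigger is an increase while the SOWS trigger is an absolute score.

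**Step 2. Illustrative participants under each rule.**

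| Baseline, later score | 7.3 definition | 7.3 SOWS row | 9.4 trigger |
|---|---|---|---|
| 15, 15 | not an AE (no worse) | AE | review |
| 15, 12 | not an AE (improved) | AE | review |
| 11, 11 | not an AE (no worse) | AE | no review |

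The first two rows show the conflict with the definition. The third shows a second mismatch: the AE rule includes a score of exactly 11 and the review trigger does not.

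**Step 3. Is a reference score available?** By 6.1 and 6.2.4, yes. The 6.2.2 note names only post-treatment and follow-ups, so the sections disagree. If baseline SOWS is taken at the early edge of its window, 2 weeks before treatment, and the opioid-free period is the minimum of 1 week, the score is obtained 2 − 1 = 1 week before that period starts. Such a participant may still have been using opioids, which limits what the baseline score represents.

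**Step 4. Size, by assumption only.** Let q be the share of participants who enter above 11 and are still above 11, without worsening, when SOWS is next given. The documents give no value for q. With the planned N = 130 (the 9.4 trigger is not limited to one arm), independence between participants and no attrition:

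- expected number = 130 × q
- chance of at least one trigger without worsening = 1 − (1 − q)^130

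| q (assumed) | Expected number | Chance of at least one |
|---|---|---|
| 1% | 1.3 | 0.73 |
| 2% | 2.6 | 0.93 |
| 5% | 6.5 | 0.999 |
| 10% | 13 | >0.999 |
| 20% | 26 | >0.999 |

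As 9.4 is worded, a single score is enough, so even a small q makes one such trigger likely. The contradiction in Step 2 does not depend on q.

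**The case against.** The strongest reply is that the SOWS row is a surveillance flag. The AE definition is worded as a general one, the table lists ways in which AEs are monitored, and the detailed rules sit in appendices that are not in the supplied text. A cut-off that over-flags errs on the side of caution, and no hypothesis, sample size or efficacy analysis depends on it. Much of this stands: an absolute score can be a reasonable prompt for clinical follow-up, and the consequence is limited to safety recording and review. It does not remove the conflict, because the row says that the score indicates an AE. Section 7.4 describes adjudication as settling severity and relatedness, not whether a baseline-level symptom counts as an AE.

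Three stronger readings are tempting, and the documents do not support them.

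- **New symptoms below the cut-off are missed.** A reader might infer that a rise from 0 to 10 goes unrecorded. The general definition still covers a new symptom, adverse events are a scheduled item in their own right, and section 8 has withdrawal symptoms monitored at all individual, group and assessment appointments.
- **The by-group review reflects who was enrolled.** Allocation is randomised 1:1, so entry scores are balanced between arms in expectation. Pre-existing scores add noise to both arms. Section 7.3 gives SOWS weekly during treatment to FORT-A participants; whether that affects the number of flagged visits by arm is a separate question on which this point does not rely.
- **Withdrawal is presumed to be caused by the research.** Section 7.3 lists only potential research-related events, and the principal investigator decides relatedness.

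It is also fair to object that one week off opioids is a minimum. Many participants may have stopped long before, so q could be small.

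**Conclusion.** The inconsistency is real and can be shown from the text alone. By the 7.3 definition, withdrawal that is unchanged or improving since baseline is not an adverse event. By the SOWS row it is one, and above 11 it also meets the 9.4 condition for review. SOWS is the only tool in the table with no provision for participants already at or above the cut-off at entry.

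How often this would occur cannot be derived from the documents. The counts above rest wholly on assumed shares and on scores persisting to a later administration; attrition or early resolution would lower them. The effect is confined to the AE record and the review process, and the main analyses are untouched.

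**What to change.** 1. Reconcile the AE definition in 7.3, the SOWS row in 7.3 and the SOWS item in 9.4, including the difference between a score of 11 or more and a score above 11. The investigators decide the AE criterion and the review trigger; none is proposed here.
2. Reconcile the SOWS note in 6.2.2 with 6.1 and 6.2.4, so that it is clear whether a baseline score is obtained.
3. In the AE record and the by-group tabulation, identify scores already present at baseline separately from new or worsened ones. State that the baseline SOWS may precede the one-week opioid-free period, so that it is read with that limit in mind.

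Clinical follow-up of high scores is unchanged. The cost is wording in 6.2.2, 7.3 and 9.4 and one extra classification in the safety table. If SOWS is given at baseline as 6.1 and 6.2.4 say, no new data are needed.

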3. STUDY DESIGN

To address the primary and secondary hypotheses, this research study was designed as a randomized clinical trial comparing the manualized FORT-A treatment to treatment as usual for polytraumatic chronic musculoskeletal pain in the STVHCS Polytrauma Rehabilitation Center. Eligible OEF/OIF/OND Veterans will be randomized to either arm in 1:1 random permuted block randomization with no stratification. Because the FORT-A is a group intervention, it is vital that we randomize into meaningful blocks of at least three Veterans and no more than seven. Three is chosen as the lower block boundary because the PI had success in the original FORT trial with FORT groups of three active duty service members. Seven Veterans will be the upper boundary because FORT groups of more than seven military members were difficult to manage. In block randomization with static boundaries, study staff overseeing randomization will lose blinding if they are aware of how many participants have already been randomized into each block. For example, if block boundaries are always 5 participants and the treatment as usual condition has 5 participants while the active treatment has 4, then the staff randomizing the 10th participant will know with certainty that this participant will be in the active treatment group. To protect blinding, we have chosen to implement a variable boundary randomization for which the study staff randomizing patients will be blind to the boundaries and the resulting condition of the participant (see Sanghaei, 2011). The PI, Independent Evaluators, and Biostatistician will be blind to the condition of all participants until data lock. A research assistant overseeing randomization will also be blinded by randomizing unique patient identifiers into variable permuted blocks (through the STRONG STAR Data Core) by unique study identifier (e.g., first participant identified as #0001). All assessments given by Independent Evaluators will be labeled with just the unique identifier. Only the study coordinator (and co-coordinator) will be able to link unique identifiers to individual participants.

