responded best to group PT on Monday, Tuesday, Thursday, and Friday with a break on Wednesday to allow for recovery. The PRC PT Service has already agreed to allow the study to use their space and equipment for study-related PT. PT providers will be encouraged to participate in FORT-A group psychotherapy sessions and STRONG STAR Interns/Fellows will be encouraged to sit in on group PT sessions (to maintain continuity in this interdisciplinary program).

Blinding: [name] or a PRC PT/OT will monitor adherence to recommended PT practice and will not share details of the PT with the PI or any other blinded research personnel.

Providers and Qualifications: PT will be provided by [name], her Physical Therapy students with WOC appointments at the VA, or existing PRC PT/OT providers. The number of students PT interventionists over time will vary and is indeterminate but will be greater than 2. Skills required for the PT portion of the treatment will include skills for rehabilitation of chronic pain, strength and conditioning, and improved range of motion for the back and extremities.

Interdisciplinary Staff Meetings (Manual Under Development)

The entire study team (with the exception of IEs) will meet weekly to discuss progress of FORT-A participants and PRC participants. Participants will be discussed without identifiers (even using the unique identifier would unblind the PI to the condition of the participant. These meetings will be run by the research coordinator and/or co-coordinator who will be aware of patient identity in case an adverse event is noted and needs to be addressed. Issues discussed in these weekly meetings include adherence to protocol, treatment goals, problems with treatment, and changes in medication or medical status. These meetings will occur from 1200-1300 in the PRC with the VA PI's ([name], [name]) in attendance.

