Blinding: Cases will only be discussed in a deidentified fashion to avoid unblinding the PI (who must be present at these meetings to assess progress of the study, troubleshoot procedural difficulties, and offer expert clinical guidance on implementing the program. To accomplish this, the team will develop a set of identifiers for participants specific to these staff meetings that are discreet from their research unique identification number. The study coordinator/co-coordinator will maintain a link for these identifiers to ensure continuity (NOTE: THIS MAY BE TOO CONVOLUTED TO IMPLEMENT, SO WE MAY WANT TO CONSIDER SOME OTHER WAY – PERHAPS USING PARTICIPANT INITIALS, WHICH WOULD BE MEANINGLESS TO THE PI).

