Homework: Group Individual Psychotherapy PT	8/10 practice sessions 4/5 trauma rehearsals 2/2 weekend flowsheets	Give opportunity for practice/trauma rehearsal before class

Study interventionists will maintain study activity logs (see **Appendix E**, maintained centrally by the Study Coordinator) where they will log the date and completion status of each clinical activity (including sessions attended or missed). These will be brought to weekly interdisciplinary staffing meetings where adherence will be discussed and problem-solved by the interdisciplinary treatment. The PI will attend parts of these meetings to monitor study progress and troubleshoot general problems (he cannot stay when specific patients are discussed, even by study ID, because he

would become aware of which IDs are in the FORT-A group). A study activity log example is below:

FORT-A; Week 1				
ID	Date	Activities	Attended?	Notes
10EX1	01/01/2001	Group PT IP	Y Y Y	Patient reported an injury on 01/02/2001; entered in AE log as non-study-related; consulted study MD on 01/05/2001; pt was cleared to continue
	01/02/2001	Group PT BFB	Y Y Y	
	01/03/2001	---- Rest Day ----		
	01/04/2001	Group PT IP	Y N Y	Patient given an extra flowsheet for the evening of 01/05/2001 to make up that missed session; BFB missed on 01/05/2001 and was rescheduled for next week
	01/05/2001	Group PT BFB	Y N N	

Participant adherence to assessments. Adherence to assessments is vital to this work. For this research, assessment is broken into 3 distinct categories (psychosocial, functional, opioid). Most assessments are administered at pre-treatment, post-treatment, 6-month follow-up, and 12-month follow-up. A few measures are ongoing. Adherence to assessment is defined as completion of assessments within a specified window of time. Categories of assessment, assessment windows, and managing adherence to assessments are as follows:

FORT-A Assessment Category	Assessment Window	Tips to Promote Adherence
Psychosocial Assessments	Pre-treatment/Baseline * ≤ 2 weeks before treatment	Schedule pre- and post-tx assessment with first and last days of tx
Functional Capacity Assessments	Post-treatment * ≤ 2 weeks after Tx completed	
Opioid Assessments	6-month follow-up *24 weeks (± 2 weeks) after Tx completed	Reminder/check in phone calls every month
	12-month follow-up *50 weeks ± 2 weeks after Tx completed	Psychosocial and FCE scheduled on same day

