10. DATA COLLECTION AND QUALITY ASSURANCE

10.1 Data Collection Forms

Data will be collected by an Independent Evaluator blind to the randomized condition of the participant and entered into an online SQL database on the STRONG STAR server that is designed specifically for this study. As described in the STRONG STAR Data Entry SOP (see **Appendix S**), data are double-entered to minimize transcription errors and all data entry forms include appropriate data entry masks that limit the format and scope of entered data (to ensure that out-of-range values are not erroneously recorded) with provided feedback if entered data exceed expected ranges. STRONG STAR has developed strict rules guiding the translation of assessment measures and data recording forms into digital formats as outlined in **Appendix T**. Paper copies of assessments are also uploaded and tagged to the assessment record for review by the IEs or other study staff if adjudication of responses is needed. The STRONG STAR Network is FISMA compliant and has received permission from the VHA for the storage of Veteran study data (which is very strictly controlled by the VA system). Because the STRONG STAR Database is accessible through a secure internet portal, data can be entered into the system directly from any VA computer with internet access (of which this study currently has dedicated access to two through the PRC). To ensure confidentiality of patient records, all data are entered into study records using the participant's unique ID. A link between identifiers and the ID is maintained in a separate data table with access restricted to individuals who are not blind to patient identifiers (e.g., study Coordinator, interventionists).

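### Section 7.3 makes no exception for the blinded Independent Evaluators at the weekly meeting on adverse events and participant status, so an evaluator may learn a participant's arm before a later TLFB interview

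*Combined protocol and SAP*

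**What the plan says.** Section 7.3 describes a weekly research meeting, held on Thursdays from 1030 to 1100 in the STRONG STAR Conference Room. Its purpose is "to discuss research progress and to discuss participant status and flow throughout the research process", and on safety it adds: "All Adverse Events (AEs) and Serious Adverse (SAEs) will be discussed at these meetings (attended by all study staff". The blinding safeguard given there is one sentence: "To protect blinding, participants will be discussed by unique identifier only".

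Section 3 requires the IEs to be blind to condition until data lock, and also says: "All assessments given by Independent Evaluators will be labeled with just the unique identifier". Section 10.1 repeats the blinding requirement: "Data will be collected by an Independent Evaluator blind to the randomized condition of the participant".

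Section 5.2 describes a second weekly meeting, the interdisciplinary staff meeting, held from 1200 to 1300 in the PRC: "The entire study team (with the exception of IEs) will meet weekly to discuss progress of FORT-A participants and PRC participants". Section 7.2 says that treatment-note data go to the weekly research meeting, and names the PI and Co-Investigators as those present. Section 6.2.3 has the coordinator attend every study meeting and help to preserve blinding.

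**The concern.** Participants and treatment providers cannot be masked in this trial, as Section 9.2 acknowledges. The masked evaluator is therefore one of the few remaining protections against biased outcome assessment.

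A unique identifier hides identity from someone who cannot connect it to a person. An IE can make that connection, because the IE sees the participant and records the assessment under that identifier. An adverse event discussed against an identifier is, to an IE, an event in a person the IE has assessed or will assess. If the discussion shows that the event arose in a FORT-A session, the IE knows the arm at every later visit.

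The outcome most at stake is the TLFB. Section 9.5.2 makes it the primary opioid endpoint and describes a semi-structured interview in which a masked IE guides the participant's recall of daily use. An interviewer who knows the arm can influence how far that recall is probed.

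**Working it through.** No formula or stated figure applies. The check is whether the passages, read together, leave a route by which an IE could learn the arm.

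1. **Are IEs among those who attend?** Section 7.3 says all study staff and excepts no one. Section 5.2 had to except IEs from the entire study team, which implies that they belong to it. The natural reading of 7.3 includes them.

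2. **Does the exclusion in 5.2 carry over?** No. The two meetings differ in time (1200-1300 against Thursday 1030-1100), place (PRC against STRONG STAR Conference Room) and purpose. Section 7.3 does not refer to the rule in 5.2.

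3. **Does the identifier protect the IE's blind?** Section 3 puts the same identifier on the IEs' assessments, and Section 5.4 has evaluators keep their assessment logs by it. It does not separate an IE from the participant.

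4. **Can the content reveal the arm?** The monitoring table in 7.3 gives these checks during treatment for FORT-A participants. The session counts come from Section 5.1.
   - Pain rating at each physical therapy appointment: 4 per week × 3 weeks = 12 appointments.
   - PCL-5 at each individual PTSD session: 2 per week × 3 weeks = up to 6. There may be fewer if another clinic provider gives the individual sessions.
   - PHQ-9 once a week: 3.
   - SOWS once a week: 3.

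   The total is 12 + 6 + 3 + 3 = up to 24 scheduled checks per FORT-A participant between baseline and post-treatment. For PRC participants the table schedules none in that interval; both arms are measured at the assessment visits. An event triggered by one of these scores, and described as arising in a session or dated within the treatment weeks, therefore points to FORT-A. An event reported with neither source nor timing does not.

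5. **Does the IE assess the participant afterwards?** Yes. The TLFB follows at post-treatment and at the 6- and 12-month visits, with monthly TLFB assessments by telephone between them (Section 6.2.4). Section 9.5.2 assigns TLFB administration to a masked IE. Section 9.5.1 has a blinded IE administer the ODI, but that is a self-report form with fixed response anchors.

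The route exists on the text of 7.3. How often it would be used cannot be worked out from the documents.

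**The case against.** The strongest reply is that attendance is not settled. Section 7.2 lists only the PI and Co-Investigators for the weekly research meeting, and the blinding diagram (Figure 2) and the adverse-event SOPs are not available here. In addition, Section 6.2.3 gives the coordinator a duty at every meeting to help keep the blind and has all staff briefed on it. Both points are fair. The first shows an inconsistency that needs resolving rather than a safeguard. The second is a general duty that does not remove IEs from the room. Section 6.2.3 also tells the coordinators to use unique identifiers when speaking with IEs, which does not shield an IE who knows whose identifier it is.

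A reader might infer that any mention of an identifier at this meeting reveals the arm, because Section 5.4 says of the PI that "he cannot stay when specific patients are discussed, even by study ID". The documents do not support that. Section 5.4 concerns a treatment staffing at which interventionists bring FORT-A session logs, so hearing an identifier there places it in FORT-A. The 7.3 meeting covers events in both arms, including unrelated ones such as influenza or a new injury. PRC participants may also receive physical therapy or counselling, so a complaint linked to therapy is not unique to FORT-A.

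A reader might also want to convert the risk into an inflated false-positive rate. That would need an assumed interviewer effect and an assumed share of participants discussed, and the documents give neither. A shift applied to a whole arm would overstate a problem confined to the participants discussed.

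Finally, the TLFB has secondary checks: MEMS caps, the VA record and the Texas prescription database. They help to detect distortion, but they do not replace a masked interview as the primary opioid measure.

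**Conclusion.** The concern holds as a gap in the blinding procedure. As written, 7.3 admits evaluators who must stay blind to a discussion that can reveal the arm, under an identifier they can attach to a person. Section 5.2 already excludes them from the comparable meeting.

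The size is limited. The risk falls on participants whose treatment-phase events or status are discussed in enough detail to show source or timing. It bears mainly on the TLFB and hence on Aim 2. The ODI is less exposed, because unmasked participants complete it themselves, so the documents do not support a claim that the primary outcome is compromised. Unblinding is possible, not certain, and its effect on the results cannot be quantified from the documents.

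The conclusion rests on two readings: that IEs count as study staff, and that the attendance statement in 7.3, not the one in 7.2, describes practice. If 7.2 is the accurate description, the correction is one of wording only.

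**What to change.** In Section 7.3, amend the attendance statement so that all study staff attend except the Independent Evaluators, as Section 5.2 does for the staff meeting. Revise Section 7.2 so that both sections give the same attendance for the weekly research meeting.

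Safety reporting does not depend on IEs being present: 7.3 already requires any study member who identifies an event to report it immediately to the coordinator. The cost is a short text change in two sections, and IEs miss the participant-level part of a 30-minute meeting.

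Section 5.2 also proposes that "the team will develop a set of identifiers for participants specific to these staff meetings". That need not be extended to 7.3 for this purpose. Once IEs are excluded it adds nothing to their blind, and 5.2 itself doubts that the scheme is workable.
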